4.1 Management of Optical Correction

A refraction should be performed whenever the investigator suspects that refractive error may not be optimally corrected.

4.2 Management of Strabismus

Strabismus surgery is allowed at the discretion of the investigator. Surgery will be recorded in the comment section of the Follow-up Examination Form.

4.3 Worsening of Visual Acuity in the Amblyopic Eye

If visual acuity should worsen in the amblyopic eye (or in the sound eye and does not recover with cessation or reversal of treatment), the investigator should evaluate this condition using best clinical judgment and perform whatever work up is clinically indicated to assess for an alternate cause (i.e., other than amblyopia) for the visual loss. Patients found to have a cause other than amblyopia that fully explains the visual loss (i.e., amblyopia was never present) will be dropped from the study.

4.4 Patient Withdrawals

A patient (and in this case the parents or guardian) may withdraw from the trial at any time. This is expected to be a very infrequent occurrence in this trial in view of the testing procedure's similarity to routine clinical practice. If the parents or guardian indicate that they want to withdraw the child from the study, the investigator personally should attempt to speak with them to determine the reason.

4.5 Risks

There are no risks involved in this study that would not be part of usual care.

4.5.1 Risks of Examination Procedures

The procedures in this study are part of daily pediatric eye care practice in the United States and pose no known risks. As part of a routine usual-care exam, the patient may receive cycloplegic/dilating eye drops.

4.5.2 Risk of Patching

The risks involved in the study are identical to those that would be present for a patient treated with occlusion therapy with patching who is not participating in the study.

In view of the small number of hours of daily patching, significant skin irritation is unlikely. If irritation occurs, the parent will be advised to put an emollient on the skin and discontinue use of the patch for a day.

Patching potentially could decrease the visual acuity in the sound eye, although this is almost always reversible. However, this occurrence is extremely unlikely in view of the small number of hours of daily patching. The diagnosis and management of reverse amblyopia is left to the investigator's judgment.

Patching could precipitate the development of an ocular deviation, although this has been found to be very rare in our previous studies and indistinguishable from the natural history of the condition. If treatment precipitates the development of an ocular deviation (e.g., esotropia in child with hyperopia), the parent will be advised to have the patient see the investigator as soon as possible.

669
670 There are some activities that should not be performed when patched due to the level of vision in
671 the amblyopic eye, such as riding a bike, in-line skating, skateboarding, or other activities in which
672 the patient could get hurt. The consent form will explicitly instruct parents not to allow their child
673 to perform such activities while patched.

674 **4.5.3 Risk of Bangerter Filters**

675 The risks involved in the study are identical to those that would be present for a patient treated with
676 Bangerter filters who is not participating in the study.

677
678
679 The more dense Bangerter filters potentially could decrease the visual acuity in the sound eye,
680 although this is almost always reversible. However, this occurrence has not been reported. The
681 diagnosis and management of reverse amblyopia is left to the investigator's judgment.

682
683 There are some activities that may require extra caution when using the Bangerter filter due to the
684 level of vision in the amblyopic eye and blurring in the sound eye. These activities include riding a
685 bike, in-line skating, and skateboarding. The consent form will instruct parents that the child may
686 require more supervision when performing these activities.

687 **4.6 Reporting of Adverse Events**

688 Each investigator is responsible for informing his/her IRB of serious treatment-related adverse
689 events and for abiding by any other reporting requirements specific to his or her IRB.

690
691 Data on the complications of the study treatments will be tabulated regularly by the Coordinating
692 Center for review by the Steering Committee. Serious complications will be reported expeditiously
693 to the Data and Safety Monitoring Committee, which will receive a full adverse event report semi-
694 annually. Following each DSMC data review, a summary will be provided to IRBs.

695 **4.7 Patient Payments**

696 The parent/guardian of each patient will be compensated \$25 for completion for each protocol-
697 specified follow-up visit to a maximum of \$100. If there are extenuating circumstances, additional
698 funds may be provided for travel if expenses exceed \$25 and the patient will be unable to complete
699 the visit without the reimbursement of the travel expenses. All payments will be made by the Jaeb
700 Center by the month following the date of each completed visit.

701 **4.8 Discontinuation of Study**

702 The study may be discontinued by the Steering Committee (with approval of the Data and Safety
703 Monitoring Committee) prior to the preplanned completion of enrollment and follow-up for all
704 patients.

705 **4.9 Contacts by the Jaeb Center for Health Research**

706 The Jaeb Center serves as the PEDIG Coordinating Center. The Jaeb Center will be provided with
707 the parent/guardian's contact information. The Jaeb Center staff will be contacting the
708 parent/guardian by phone to facilitate visit scheduling. A patient newsletter and study updates may
709 be sent. Patients will be provided with a summary of the study results in a newsletter format after
710 completion of the study by all patients.

CHAPTER 5: SAMPLE SIZE ESTIMATION AND STATISTICAL ANALYSIS

The estimation of sample size and statistical analysis plan are summarized below and detailed in separate documents. A detailed statistical analysis plan will be written and finalized prior to the completion of the study. The analysis plan synopsis in *section 5.2* contains the framework of the anticipated final analysis plan, which will supersede *section 5.2* when it is finalized.

5.1 Sample Size Estimation

The sample size estimate has been computed for the primary study objective, to determine whether the visual acuity improvement at 24 weeks obtained with Bangerter filters is at least as good (noninferior) as the improvement obtained with patching, in concert with the analytic approach for this objective (analysis of covariance) as described in *section 5.2*.

Based on data from previous ATS studies (ATS1, ATS2, ATS3, and ATS5), we assumed a standard deviation for the 24-week outcome score of 0.16 logMAR and a correlation between baseline and 24-week outcome score of 0.20.

To select a sample size for this trial, it is necessary to set the non-inferiority limit, which represents the end of a 95% confidence interval for the difference in mean acuity between groups. A limit of 0.075 logMAR (3.75 letters) was considered by the Planning Committee to provide sufficient evidence for non-inferiority. Because the primary objective is to determine whether Bangerter filters are as effective as patching, non-inferiority of the Bangerter filters will be declared if the upper limit of a 1-sided 95% confidence interval constructed on the difference between adjusted mean visual acuity scores for the two groups (Bangerter filter – Patching) is less than the specified non-inferiority limit.

For a 0.075 logMAR non-inferiority limit, a 1-sided 95% confidence interval, 90% power, a standard deviation of 0.16 logMAR and correlation between the baseline and outcome acuities of 0.20, the sample size of moderate amblyopes required for the study was estimated to be 152, equally divided between the two groups. This was increased to 170 to account for up to 10% loss to follow-up.

5.2 Primary Analysis

Non-inferiority of the Bangerter filters will be declared if the upper limit of a 1-sided lower 95% confidence interval constructed on the difference between adjusted mean visual acuity scores for the two groups (Bangerter filter – Patching) is less than the specified non-inferiority limit of 0.075 logMAR.

The adjusted means mentioned above will be obtained through application of an Analysis of Covariance (ANCOVA) model using baseline visual acuity scores as the covariate and 24-week visual acuity scores as the dependent variable. A 1-sided confidence interval will be formed on the difference between 24-week visual acuity mean scores after these means have been adjusted for the baseline acuity scores.

The primary analysis approach will be developed in conjunction with the DSMC.

759 **5.3 Secondary Analyses**

760 **5.3.1 Time Course of Visual Acuity Improvement with Bangerter Filters**

761 A secondary analysis will be performed to determine the time course of visual acuity improvement
762 with Bangerter Filters and compare this improvement with the time course of visual acuity
763 improvement with patching.

764
765 A Cox proportional hazard model will be used to compare the time until visual acuity improvement
766 across treatment groups, adjusting for baseline visual acuity. Visual acuity improvement will be
767 measured as time to 20/25 or better visual acuity of the amblyopic eye
768

769 A random effects model will be used to compare time to visual acuity improvement. A regression
770 line for each individual will be fit for visual acuity over time. Then the average slope in the
771 Bangerter filter group will be compared to the average slope in the patching group.
772

773 A population-averaged model will also be used to compare time to visual acuity improvement. The
774 average visual acuity at each time point will be calculated for the Bangerter filter and patching
775 groups separately. Then a regression line will be fit for the mean visual acuity in each treatment
776 group over time, and the slopes of these lines will be compared. A comparison of mean visual
777 acuity by treatment at each time point also will be performed by fitting a discrete time model and
778 using linear contrasts.
779

780 Prior to performing the random effects or population-averaged mixed model analysis, exploratory
781 analyses will be performed to determine the time course of improvement in visual acuity over time
782 and the correlation structure of the data. These will be used (1) to guide choice of the correlation
783 structure for the population-averaged model and (2) determine whether data transformation is
784 needed to linearize the relationship between time and visual acuity improvement.
785

786 **5.3.2 Impact on Quality of Life**

787 A secondary analysis will be a treatment group comparison of scores obtained on the modified
788 Amblyopia Treatment Index (ATI) 24 weeks after randomization. Given that the questionnaire will
789 have been modified, the first step will be to conduct a factor analysis to confirm whether the same
790 factor structure still applies. Assuming the same factors are confirmed, the average of the item
791 responses over each factor will be calculated and compared by treatment group with a t-test for
792 difference in means.
793

794 **5.3.3 Predictive Value of Blur**

795 A secondary analysis will be performed, limited to patients in the Bangerter filter group, to
796 determine whether blurring the sound eye visual acuity with Bangerter filters is predictive of visual
797 acuity improvement. The amount of blur will be explored in two ways:

- 798 ○ a continuous measure of the degradation in sound eye acuity with the filter
- 799 ○ a dichotomous variable indicating if sound eye acuity with the filter is worse than
800 the amblyopic eye acuity.

801 Descriptive data and simple linear regression models will be used to explore the relationship
802 between blur measured at each follow-up visit and the corresponding change in amblyopic eye
803 visual acuity from the previous visit, adjusting for the amount of blur at the previous visit. If the
804 estimated effect of blur looks consistent, a longitudinal model with both measures of blur as time
805 dependent covariates will be used.

806 **5.3.4 Predictive Value of Fixation Preference**

807 A secondary analysis will be performed, limited to patients randomized to the Bangerter filter
808 group, to determine whether a change in fixation preference is predictive of visual acuity
809 improvement in patients with amblyopia. Two variables will be created:

- 810 ○ Fixation preference with the Bangerter filter
- 811 ○ Switch in fixation preference – in which possibilities for the data are all
812 combinations of fixation preference with and without the Bangerter filter.

813 Descriptive data will be used to explore the relationship between fixation preference and change in

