217 **1.2 Study Objectives**

- 218 • Primary: To evaluate the non-inferiority of Bangerter filters to 2 hours of daily patching as a
219 primary treatment for moderate amblyopia (20/40 – 20/80) in children ages 3 to <10 years.
- 220 • Secondary:
 - 221 ○ To determine the time course of visual improvement with Bangerter filter treatment.
 - 222 ○ To compare patient quality of life, measured by a modified Amblyopia Treatment
223 Index, between patients treated with patching vs. Bangerter filters.
 - 224 ○ To determine whether the degree of blurring of sound eye visual acuity relative to
225 the amblyopic eye visual acuity predicts improvement in acuity.
 - 226 ○ To determine whether fixation preference is predictive of improvement in visual
227 acuity.

228

229 **1.3 Synopsis of Study Design**

230 Major eligibility criteria (see section 2.2 for a complete listing)

- 231 • Age 3 to < 10 years
- 232 • Amblyopia associated with strabismus, anisometropia, or both
- 233 • No ocular cause apparent for reduced visual acuity
- 234 • Visual acuity 20/40 – 20/80 (71 to 54 letters inclusive) in amblyopic eye
- 235 • Visual acuity 20/40 or better (≥ 69 letters) in sound eye
- 236 • Interocular difference ≥ 3 logMAR lines (≥ 15 letters)
- 237 • No amblyopia treatment other than spectacles in last 6 months
- 238 • Currently wearing spectacles
- 239 • Appropriate spectacles have been worn for 16 weeks prior to enrollment or visual acuity
240 documented to be stable
- 241 • No myopia > -6.00 D spherical equivalent in either eye
- 242 • Cycloplegic refraction within 6 months prior to enrollment

243

244 Treatment Groups

245 Patients will be randomized to two treatment groups:

- 246 • 2 hours daily patching of the sound eye plus one hour near activities while patching
- 247 • Bangerter filter worn on sound eye spectacle lens full time (0.3 for 20/40-20/63 and 0.2
248 for 20/80) plus at least one hour near activities

249

250 Sample Size

251 170 patients (85 per group) with moderate amblyopia (20/40 to 20/80)

252

[figure not shown]
253

254 Visit Schedule

[figure not shown]
- 255 • 6 weeks \pm 2 weeks
256 • 12 weeks \pm 2 weeks: Increase intensity of treatment if acuity not improved 1 line (5 letters) or
257 more from baseline (*see section 3.4.2*)
258 • 18 weeks \pm 2 weeks: Increase intensity of treatment if acuity not improved 2 lines (10 letters) or
259 more from baseline and intensity of treatment not increased at 12 week visit (*see section 3.4.3*)

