3.3 Follow-up Visit Schedule

All patients will have the following study visits after randomization:

- Visit A: 6 weeks \pm 2 weeks
- Visit B: 12 weeks \pm 2 weeks
- Visit C: 18 weeks \pm 2 weeks
- Visit D: 24 weeks \pm 2 weeks

Additional visits can be performed at the discretion of the investigator. A Follow-up Examination Form should be completed on the study website for every exam (not just the minimum required exams).

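### Section 5.3.3 fits the longitudinal blur model only if the visit-level estimates from the same data look consistent, with no criterion, so the results decide whether the pooled answer is produced

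*Protocol*

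**What the plan says.** Protocol section 1.2 lists the objective as "To determine whether the degree of blurring of sound eye visual acuity relative to" the amblyopic eye predicts improvement in acuity. Section 5.3.3 gives the analysis: "A secondary analysis will be performed, limited to patients in the Bangerter filter group, to" establish whether blur is predictive.

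Two measures are listed. One is continuous: how far the filter degrades sound-eye acuity. The other is dichotomous: whether the filtered sound eye sees worse than the amblyopic eye.

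The first step always takes place: "Descriptive data and simple linear regression models will be used to explore the relationship" between blur at each follow-up visit and the change in amblyopic-eye acuity since the previous visit, adjusted for blur at that previous visit. Section 3.3 schedules four follow-up visits (6, 12, 18 and 24 weeks).

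The second step is conditional. If the "estimated effect of blur looks consistent, a longitudinal model with both measures of blur as time" dependent covariates is used. The protocol does not say what counts as consistent, who judges it, or what answers the objective if the condition is not met.

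**The concern.** The condition depends on the estimated effect, and that estimate comes from the data that the longitudinal model would then analyse. Two investigators with the same eight visit-level coefficients (4 visits × 2 measures) could reasonably differ on whether to fit the model.

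Section 5.3.1 is a useful contrast. There, exploratory work guides the correlation structure and a possible transformation, but the models are fitted whatever it shows. In 5.3.3 the exploratory result decides whether the pooled model is fitted at all.

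Two things are at stake. If the gate favours estimates that agree in direction, chance agreement also favours a significant pooled result, so a reported longitudinal p-value can overstate the evidence. If blur does matter, sampling noise at one visit can close the gate and the planned pooled answer is never produced.

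**Working it through.** **The plan's own figures.** The protocol gives no sample size, power or significance level for the blur analysis. Its only such figures belong to the primary comparison (section 5.1), and they reproduce:
- Per arm, 2 × (1.645 + 1.282)² × SD² / 0.075².
- SD 0.16 gives 78 per arm (156 in total). SD 0.16 × √(1 − 0.20²) gives 75 per arm (150 in total). The plan states 152.
- 152 / 0.90 = 169, against 170 stated.

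Nothing there is in question.

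**Inputs for the gate.** From the protocol: four follow-up visits, and a gate described only as looking consistent. Assumed, because the protocol gives no figures: four independent, equally precise visit estimates z₁ to z₄ for one blur measure; pooled statistic P = (z₁ + z₂ + z₃ + z₄)/√4; two-sided 5% test. There were 2,000,000 simulated trials with no blur effect.

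**Gate probabilities that can be checked by hand.**
- All four signs agree: 2 × (1/2)⁴ = 0.125.
- At least three of four agree: 2 × (1 + 4)/16 = 0.625.

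**Results with no blur effect.** The last column is the product of the two before it.

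| Reading of consistent | Gate opens | Pooled test significant, given model run | Significant longitudinal result, all trials |
|---|---|---|---|
| Homogeneous (Cochran Q p > 0.10) | 0.900 | 5.0% | 4.5% |
| Homogeneous (Cochran Q p > 0.50) | 0.50 | 5.0% | 2.5% |
| At least 3 of 4 same sign | 0.625 | 7.9% | 4.9% |
| All 4 same sign | 0.125 | 26% | 3.2% |
| All 4 same sign and at least one visit significant | 0.023 | 73% | 1.7% |

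If the model is always fitted, the rate is 5%. If adjacent visit estimates are correlated at +0.3 or −0.3, the 26% becomes 20% or 31%.

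A separate simulation (76 children, the 5.3.3 visit regressions, within-child blur correlation 0.3 to 0.7, independent acuity changes) gave 25% to 27% for the all-four reading, with the gate open in about 13% of trials.

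**Results with a true effect.** Let the always-fitted pooled test have 80% power.
- Mean of P = 1.960 + 0.842 = 2.802.
- Mean of each visit estimate = 2.802/√4 = 1.401.
- Chance that one visit has the right sign = Φ(1.401) = 0.919.
- All four right: 0.919⁴ ≈ 0.71, so the model is not run in about 29% of trials.
- At least three of four agree: 0.714 + 4 × 0.777 × 0.081 + 0.002 (three or four agreeing in the wrong direction) ≈ 0.97, so it is not run in about 3%.
- Homogeneity gate: Cochran Q does not depend on the size of a common effect, so the model is unrun in 10% or 50% of trials for the two thresholds shown.

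**The case against.** The strongest defence is that the ordinary meaning of consistent, before pooling visits, is that the effect is similar from visit to visit. A gate of that kind leaves the pooled test at 5%. The section also calls its work exploratory ("acuity improvement. The amount of blur will be explored in two ways"), states no significance level, and is confined to one arm. The visit-level regressions are done regardless, so a reader could see what opened or closed the gate. Chapter 5 says that details are in separate documents.

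Much of this stands, and it rules out several stronger conclusions that a reader might draw:
- *That the longitudinal p-value is invalid.* The protocol does not say same sign or significant. The inflation to 26% belongs to one possible reading.
- *That false-positive longitudinal findings become more frequent.* Across all trials they stay at or below 5% under every reading tried.
- *That evidence of no effect is never pooled.* Four estimates near zero are consistent in the homogeneity sense and would be pooled. Even under the all-four gate, about three quarters of the null models that are run are non-significant.
- *That eight uncorrected tests give about a 30% chance of a false finding.* The protocol plans descriptive data and regressions. It does not name eight significance tests.

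The appeal to a later document does not remove the point. The conditional rule is written into the protocol, so this is not an omitted detail. The sentence in Chapter 5 on being superseded names section 5.2 only.

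**Conclusion.** The point holds in a limited form. The pooled answer to a named secondary objective is produced or withheld by an undefined judgement on the estimates themselves. Depending on how that judgement is read, the conditional false-positive rate is nominal (5%), slightly raised (8%) or about five times nominal (26%). A true effect that could be detected with 80% power would go unmodelled in about 3% of trials under the three-of-four reading and 29% under the all-four reading. The protocol does not choose between these readings, and that is the defect.

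The figures rest on assumed independence and equal precision of the visit estimates, on a single blur measure, and on a two-sided 5% test, none of which the protocol states. The primary non-inferiority conclusion is untouched. This is a modest weakness in a secondary analysis, worth correcting because the correction is nearly free.

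**What to change.** In section 5.3.3 and the analysis plan:
- Delete the condition and fit the longitudinal model whatever the visit-level results.
- Assess consistency over time as a blur-by-visit interaction inside that model.
- Present the visit-level regressions as descriptive estimates with confidence intervals.
- Name in advance the blur term that answers the objective. Section 1.2 asks about blur relative to the amblyopic eye, and of the two listed measures only the dichotomous one makes that comparison. The continuous measure compares the sound eye with itself, so naming it as the lead term would not match the objective.
- Label the other measure as supportive.

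This takes a few sentences and no new data. The small cost is that an association seen at a single visit, or only with the other measure, becomes exploratory.
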